An opportunity sample of participants will be recruited through their clinician or self-referral. This study will recruit participants from South London and Maudsley NHS Foundation Trust (SLaM) who are receiving care within the primary care Improving Access to Psychological Therapies (IAPT) services and secondary care perinatal services in Lambeth, Southwark, Lewisham and Croydon. The student researcher will have no prior relationship with the participants. The research team will share information with clinicians about Baby CHAT and the study procedures, so that they have a good understanding of the study before they are asked to give their patients information about the research. Clinicians will provide eligible clients with a flyer (see Appendix 2 for flyer) and, if a client is interested, will ask for verbal consent for the student researcher to contact them by phone (just name and phone number provided at this stage). To enable self-referral, posters will be placed in the waiting areas of relevant services. Posters will also be placed in maternity scanning clinics at King's College Hospital and St Thomas' Hospital, for participants to self-refer. The study will also be advertised through carefully selected online groups, social media channels and the King's College London research participation email circular.

Once a potential participant has self-referred or consented to be contacted via their clinician, the student researcher will contact them to check eligibility, introduce the project, provide the information sheet and to answer any questions. Participants will have sufficient time to consider whether they consent to take part. Participants will be offered £20 in reimbursement for taking part in the study.

Inclusion criteria

Participants eligible to take part in the project will be women aged ≥ 18 years who are pregnant, between 20- and 34-weeks' gestation, and currently experiencing depressive symptoms as identified by the EPDS. Those scoring >13 will be eligible to take part in the study. Both first-time and experienced parents will be eligible to participate.

Given the study involves the participation of potentially vulnerable individuals, all participants must be resident in or accessing services in a London borough served by SLaM, in order to facilitate access to local mental health services if needed.

Exclusion criteria

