Although this study is exploratory due to the novelty of the intervention, within feasibility research it is appropriate to set a priori thresholds for the main feasibility and acceptability outcomes. Feasibility thresholds will be as follows: 30 or more potential participants express interest in the study (participant uptake); 20 or more participants attend Baby CHAT (participant retention); and at least 70% of participants complete the study measures (missing data). The acceptability of Baby CHAT will be assessed by the feedback form, which consists mostly of open-ended questions. These will be analysed qualitatively and therefore no specific acceptability thresholds will be set.

Effect sizes for primary and secondary outcome measures will be calculated using Cohen's d. These effect sizes will inform the sample size calculations of future larger-scale studies on Baby CHAT.

Items on the outcome questionnaires will be designated as mandatory on the online survey portal, Qualtrics, to minimise missing data. Participants will be contacted to attempt to complete any missing items from other forms. Therefore, no statistical imputation methods will be required to correct for missing data.

Any deviations from the original statistical analysis plan will be reported in a protocol amendment.

4. Study procedures

Informed consent procedure

All interested participants, whether they self-referred to the study or consented to be contacted via their clinician, will have an initial contact with the research team to ask any questions about the project. Participants will be sent a full Participant Information Sheet by email to read and consider. The information in the Participant Information Sheet and opportunity for further discussion with the research team will allow detailed explanation of the aims, methods, anticipated benefits and potential harms of the study, as well as the participants' right to refuse involvement in the study and to withdraw consent at any time. The research team will ensure adequate time for each participant to consider their consent to take part. Individuals who agree to take part will then be asked to complete and return a signed consent form. All participants will receive a copy of their signed consent form.

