Following informed consent, the depression screening measure (the EPDS) will be conducted. Participants will be informed in a timely and sensitive manner whether they have met the criteria

to be included in the study. Participants who consent but do not score above the threshold on the screening questionnaire will be signposted to appropriate sources of support (as above, see Exclusion criteria).

Study schedule

Following inclusion in the study (i.e. having completed informed consent and scored over the screening threshold), participants will be asked to complete the baseline set of outcome questionnaires via Qualtrics (Time 1). Once completed, the participant will be booked into an upcoming session of the Baby CHAT group.

Participants will attend an online Baby CHAT group at a time that is convenient for them. Up to eight women will be invited to each group, to facilitate optimal group dynamics and engagement with the group content. See below for further details of the intervention.

After attending Baby CHAT, participants will be asked to complete the post-intervention outcome questionnaires and feedback form within 48 hours of the group (Time 2). One month later, participants will be contacted to complete the final follow-up questionnaires (Time 3).

Measures

The primary clinical outcome will be prenatal bonding as measured using the Maternal Antenatal Attachment Scale (MAAS). Secondary clinical outcomes of RF and depressive symptomology will be measured using the Prenatal Parental Reflective Functioning Questionnaire (P-PRFQ) and the Edinburgh Postnatal Depression Scale (EPDS). Feedback forms, containing both qualitative and quantitative components, will also be administered after participants have attended Baby CHAT in order to gather feedback on experience of the intervention (including group format, content and perceived usefulness).

Edinburgh Postnatal Depression Scale

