The EPDS (Cox, Holden & Sagovsky, 1987) is a 10-item self-report measure used to identify depression in women during the perinatal period. The scale was initially developed to screen for postnatal depression but has also been validated for use in antenatal populations (Murray & Cox, 1990). Women are asked to rate on a 4-point scale how much they have experienced symptoms over the last week. Total scores are calculated, with higher scores indicating more severe symptoms, and a score of 13 or greater indicating likely depressive illness. The final item on the scale “the thought of harming myself has occurred to me” indicates the presence of thoughts of self-harm or suicide. The EPDS has been shown to have satisfactory sensitivity and specificity (Cox, Holden & Sagovsky, 1987; Gibson et al., 2009).

Maternal Antenatal Attachment Scale

The MAAS (Condon, 1993) is a self-report questionnaire for expectant mothers, designed to assess the maternal-foetal attachment during pregnancy. The scale consists of 19 items on a 5-point Likert scale assessing women’s attitudes, feelings and behaviours towards their foetus. Most items evaluate experiences over the last two weeks, as well as imagined feelings towards the baby when they are born. An overall attachment score is calculated, as well as two subscale scores for ‘quality of attachment’ and ‘time spent in attachment mode (or intensity of preoccupation)’, for example, time spent thinking about the baby. Higher scores indicate stronger maternal-foetal attachment. The MAAS has been shown to have good construct validity (Condon & Corkindale, 1997), internal consistency and split-half reliability (Condon, 1993).

Prenatal Parental Reflective Functioning Questionnaire

The P-PRFQ (Pajulo et al., 2015) is a 14-item self-report questionnaire assessing expectant parents' abilities to think of their foetus as a separate individual with a developing temperament, personality and needs. The scale can be used during the second and third trimester of pregnancy. The 14-item measure asks expectant parents to rate several statements on a 7-point Likert scale, with higher total scores indicating higher prenatal RF. The P-PRFQ has good construct validity and showed strong concurrent validity with an established interview of prenatal parental RF (Pajulo et al., 2015), and therefore shows promising use in both clinical and research settings as a brief, cost-effective measure of prenatal parental RF.

Baby CHAT Feedback Form

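### No rule covers women who give birth before the one-month follow-up, where two scales described as pregnancy measures (MAAS and P-PRFQ) are scheduled for everyone

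*Combined protocol and SAP*

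**What the plan says.** Inclusion criteria (Section 3) admit women "between 20- and 34-weeks" of gestation. They do not say whether the upper limit applies only at entry or also on the day of the group.

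Under Study schedule (Section 4), once baseline forms are done "the participant will be booked into an upcoming session of the Baby CHAT group". No maximum wait is given. The later contact is then set: "One month later, participants will be contacted to complete the final follow-up questionnaires (Time 3". The flowchart (Section 2.3) marks the EPDS, MAAS and P-PRFQ at one month, with no condition on still being pregnant.

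Under Measures (Section 4), the MAAS is the primary clinical outcome. It is "designed to assess the maternal-foetal attachment during pregnancy" and covers "attitudes, feelings and behaviours towards their foetus". Of the P-PRFQ the protocol says: "The scale can be used during the second and third trimester of pregnancy". The EPDS is different: "The scale was initially developed to screen for postnatal depression", and it is also described as validated antenatally.

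Under Statistics (Section 3), "Items on the outcome questionnaires will be designated as mandatory on the online survey portal, Qualtrics, to minimise missing data". No imputation is planned, Cohen's d is to inform later sample sizes, and completion by at least 70% of participants is one of three pre-set feasibility thresholds.

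The text on eligibility, withdrawal, statistics, schedule, measures, end of study and the Case Report Form, and the follow-up feedback form (Appendix 6), do not mention a birth before Time 3.

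**The concern.** A woman who has delivered by Time 3 is still scheduled for two scales that ask about a foetus. If she completes them, her scores fall outside the use the protocol describes, and nothing keeps them out of a Time 3 effect size. If she does not, she is missing, and the plan has no dedicated place to record that the cause was a birth. Reasons are promised only for withdrawal.

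A birth before follow-up means that the visit falls too late for some entrants. Loss of interest means that the intervention or the burden did not hold them. A later trial needs to tell these apart, and the analyst cannot recover a birth date that was never collected.

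**Working it through.** The plan states no figure on this point, so there is none to reproduce. N = 24 rests on published recommendations and similar studies, not on a power calculation.

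**Timeline (protocol figures only)**
- One month = 365.25 / 12 / 7 = 4.35 weeks.
- Gestation at Time 3 = gestation at entry + wait for the group + 4.35 weeks.
- Entry at 34 weeks, no wait: 34 + 4.35 = 38.35, about 38.3 weeks (38.348 unrounded).
- Wait that brings this woman to 40 weeks: 40 − 38.35 = 1.65 weeks, about 12 days.

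**How many women (assumptions needed)**
The documents give no waits, birth timing or spread of entry. Assumed: entry uniform over 20–34 weeks; wait zero, or uniform over 0–2 or 0–4 weeks; birth gestation normal with mean (SD) 39.2 (1.8), 39.5 (1.6) or 40 (1.5) weeks. Women delivering before the group are removed, because the target of 24 counts attenders. Share affected = P(birth by entry + wait + 4.35 weeks, given birth after the group), by simulation with 2 million draws per cell. Ranges run across the three birth assumptions.

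| Wait | Share of attenders | Of 24 | Share of those entering at 32–34 weeks |
|---|---|---|---|
| None | 0.7–2.6% | 0.2–0.6 | 5–16% |
| 0–2 weeks | 2.6–5.9% | 0.6–1.4 | 17–33% |
| 0–4 weeks | 6.7–10.7% | 1.6–2.6 | 37–51% |

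Sensitivity: if every woman waits exactly 2 weeks, and birth is normal with mean (SD) 39.5 (1.5) or 39 (2.0), the count is 1.9–2.8 of 24. At exactly 4 weeks it is 4.7–5.3. The wait matters more than the birth assumption.

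**Effect on the 70% threshold**
Let n attend, c complete, and d be delivered women who do not complete. Compare c/n with c/(n − d).
- n = 24, d = 1: 16/24 = 66.7% and 16/23 = 69.6%, both fail; 17/24 = 70.8% and 17/23 = 73.9%, both pass. The verdict never changes.
- n = 24, d = 2: 15/22 = 68.2% still fails. At 16 completers, 16/24 = 66.7% fails and 16/22 = 72.7% passes. This is the only change.
- n = 23, d = 1: 16/23 = 69.6% fails, 16/22 = 72.7% passes.
- n = 22, d = 1: 15/22 = 68.2% fails, 15/21 = 71.4% passes.
- n = 21, d = 1: 14/21 = 66.7% fails, 14/20 = 70.0% passes.

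So one birth can change the verdict with 21–23 attenders, but only at a single completer count in each case.

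**The case against.** The strongest reply is that the design already limits the problem. Entry closes at 34 weeks and follow-up is one month, so with prompt booking even the latest entrant is at about 38.3 weeks. If the 34-week limit also applies at the group, only the no-wait row is relevant: 0.2–0.6 of 24. The high percentages describe women entering at 32–34 weeks, one-seventh of entrants under uniform entry (2 of 14 weeks). This stands, and it is why the point is minor.

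A reader might infer that mandatory items compel a delivered woman to answer about a foetus. They do not. They bind only someone who submits the form, and because participants are contacted at Time 3 the team may learn of the birth first.

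A reader might also infer that invalid scores will certainly enter the effect size. The Statistics text does not say which time points Cohen's d uses, so this is possible but not established.

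Nor can one say that a birth would go entirely unrecorded. Details of the pregnancy are collected, the Case Report Form has follow-up dates, an SAE form and a trial completion form, and SAEs that become known are documented. None of these is a dedicated field for birth before Time 3, and that is as far as the claim goes.

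**Conclusion.** The gap is real and minor. Both scales are scheduled for all participants at a time when some may have delivered, and the plan neither captures this nor says how to analyse it. The timeline arithmetic needs no outside data. The counts do: about 1 of 24 or fewer if waits are short, and about 2 or more if they are long, subject to the assumed waits, birth timing and uniform entry.

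Two parts of the study are touched. One is the secondary objective of preliminary evidence, if d is computed at Time 3. The other is the 70% completion threshold, which belongs to the primary feasibility objective. The effect there is slight, because the treatment of delivered women decides the result only at a few completer counts.

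A reader might conclude that the feasibility verdict as a whole is unsafe. The documents do not support that: the interest and attendance thresholds are unaffected, and the Time 2 forms, due within 48 hours of the group, are far less exposed.

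**What to change.** - **Time 3 survey.** Open with a sensitively worded question on whether the participant is still pregnant, with an option that covers pregnancy loss, and the date of birth if applicable.
- **Skip logic.** If she is no longer pregnant, skip the MAAS and P-PRFQ. If the baby has been born, keep the EPDS and the follow-up feedback form, whose questions do not depend on being pregnant.
- **Effect sizes.** Exclude any post-birth MAAS or P-PRFQ scores from Cohen's d. Flag post-birth EPDS scores and give the Time 3 EPDS effect size with and without these women.
- **Feasibility.** Report the number delivered before Time 3 as a result in its own right. Give the 70% completion rate with and without these women in the denominator.

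The cost is one survey question with skip logic and a few lines of analysis text. The downside is that a few Time 3 scores are lost, mainly from late entrants, so the Time 3 MAAS and P-PRFQ effect sizes apply only to women still pregnant. The report should say so.

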The facilitator will monitor participants' reactions, contributions and emotional state throughout the group. The clinician will facilitate a sensitive and validating environment if a participant experiences a low level of distress during the group. If required, the facilitator will sensitively raise any concerns about emotional wellbeing with the participant after the group in private and attempt to resolve this in collaboration with the participant. If appropriate, consent will be sought to inform their midwife of their distress. If a participant leaves the online meeting in distress, the facilitator will attempt to contact them after the group to debrief. A more senior member of the research team will be available for supervision during the times that Baby CHAT is running. See Appendix 3 for the distress pathway.

Participants will be able to contact the research team following the group for a debrief. All participants will be signposted to further information and support, including their general practitioner, midwife, local psychological therapies service, and other online resources. Information on participants' experiences of the intervention will be collected via the feedback form to support detection of adverse events.

If there is a potential safeguarding concern at any point during the study and the research team believes there may be imminent risk to the participant or another person, appropriate action will be taken (see Appendix 4 for the study safeguarding pathway). Safeguarding issues may arise during the main group, for example, if a participant mentions something concerning about themselves, their unborn baby or someone else. If this occurs, a facilitator will attempt to contact the participant after the group to gain further information and remind them of the limits of confidentiality. Risk concerns will be escalated to an appropriate member of the research team or the participant's clinical team if applicable. Some participants will already be under the care of a mental health team, while some pregnant women with a history of mental health problems may be well-known to their midwife and have more frequent contacts with the midwifery team throughout their pregnancy. If there is felt to be an imminent and serious risk to the participant or someone else, crisis or emergency services will be contacted.

Screening procedure

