The feedback questionnaire (Appendix 5) was developed as part of the initial trial on Baby CHAT with the general population (Cox et al., 2020). The form has been adapted for the purpose of this study and contains eight items, consisting of eight open-ended questions, two of which additionally have closed question components. The feedback form aims to gather participants' views on their experience of the group in order to develop it for future use, including what they liked about Baby CHAT, how helpful they found the inclusion of the 4D scan footage and anything they felt could have improved the group.

A brief, follow-up feedback form was developed for the purposes of this study's longitudinal component (Appendix 6). The form consists of four open-ended questions, one of which also contains a closed question component. The items aim to evaluate participants' experiences of the impact of the intervention over time, including anything they felt could improve the longitudinal impact and whether they have noticed any subjective changes in their mood.

Intervention

Baby CHAT is an approximately 90-minute group intervention to be delivered during pregnancy. The group is comprised of psychoeducational material about a baby's social development after birth and while the baby is growing in the womb. Attendees are encouraged to think about when an infant's social development begins and consider whether this occurs before or after birth. Participants are then shown a video clip of Reissland et al.'s (2016) study showing 4D ultrasound images of foetuses mouthing in response to sounds that are presented to them outside the womb. Reissland's research suggests that babies' social development may begin to occur as early as 32 weeks. During Baby CHAT, parents are encouraged to reflect on this information in the context of their own baby's development, including their likes and dislikes, routine and personality. The final section of the group involves generating ideas for social activities that parents can try with their baby prior to birth, such as singing to, massaging or reading to their baby. At the end, participants are asked to think about a positive take-home message from the session and, if they feel comfortable, to share this with the group. A Baby CHAT handout will be provided for participants to work through during the group and to refer to at home. See Appendix 7 for the full session plan.

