No significant changes will be made to the Baby CHAT group content for the purposes of this study. Baby CHAT was designed as a standalone session, that could be used as an add-on to existing treatments, and therefore does not target symptoms of depression specifically. However, the nature of the group discussions may naturally differ given that all participants will be experiencing depression during their pregnancy. Group facilitators will present the Baby CHAT content in a sensitive and non-blaming manner, validating participants' experiences. The facilitators will also sensitively facilitate discussions during the group around the group content, for example, anticipated difficulties engaging in new activities while experiencing depression.

While Baby CHAT was originally designed to be delivered face-to-face, in this study all sessions will be held virtually using video conferencing software. This will facilitate participants' access to the group and enable greater safety relating to the risk of Covid-19. Groups will be offered at a mixture of times, including weekdays and evenings.

End of study definition

The study will be considered completed once participants of the last Baby CHAT group have completed 1-month follow-up questionnaires. The REC will be informed once the study has ended.

6. Assessment of Safety

Adverse event reporting will take place following the intervention via the Baby CHAT feedback form. Participants will be asked if they experienced any negative effects from attending the group. These will be recorded and reported in the Annual Progress Report and copied to the sponsor.

SAEs are defined in this study as any adverse event which: results in death; is life-threatening; requires hospitalisation or prolongation of existing hospitalisation; results in persistent or significant disability or incapacity; or consists of a congenital anomaly or birth defect. SAEs are not anticipated to occur due to any of the study procedures. However, it is expected that SAEs may occur during the study for other reasons. Hospitalisation, likely due to complications with participants' pregnancies, will be considered an unrelated but expected SAE. Where SAEs are made known to the research team, these will be documented. Suspected unexpected serious adverse reactions (SUSARs) will be reported to the REC within 15 days of the Chief Investigator becoming aware.

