See Appendix 1 for further information on adverse event reporting in non-CTIMP (Clinical Trial of an Investigational Medicinal Product) research.

7. Study oversight arrangements

The joint Research & Development Office for the Institute of Psychiatry, Psychology & Neuroscience and South London and Maudsley NHS Foundation Trust will sponsor this study and provide advice when required.

8. Ethics & Regulatory Approvals

The study protocol and all other documentation will be submitted to the NHS Health Research Authority (HRA) REC.

9. Data Handling

Confidentiality

Participant's names, demographics, details of their pregnancy and past pregnancies, and contact details will be collected. Access to this information will be limited to the Chief Investigator and Co-Investigators named in this protocol. No participant-identifiable information

will be transferred outside of King's College London and South London and Maudsley NHS Foundation trust, nor outside of the EU. Participants have the right to revoke their authorisation for the use of their identifiable information. In the write-up and publication of this research, all participants will be anonymised.

Case Report Form

The Case Report Form (CRF) will record the following for each participant: unique participant identifier, confirmation of consent, demographics, eligibility criteria checklist, screening questionnaire, study procedure dates, follow-up outcome dates, any study interventional delays, AEs log, SAE form, withdrawal from study form (if applicable) and trial completion form. The Co-Investigators named in this protocol will be responsible for the completion of the CRF at the point of participant registration to the study and after each trial procedure. The CRF will be stored electronically on a secure computer network and archived after study completion as outlined below.

Record Retention and Archiving

Participants' details and consent forms will be stored electronically on a secure computer network. A unique participant ID number will be assigned to each participant, which can only be decoded by a member of the research team. This data will be password protected for additional security. Participant information collected via Qualtrics (demographics, details of pregnancy, outcome questionnaires and feedback form) will be password protected and only accessible to the research team.

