Appendix 4 – Safeguarding pathway

Appendix 5 – Feedback Form

Participant ID:

Baby CHAT Group Feedback

Thank you for coming to Baby CHAT.

We would really like your feedback on Baby CHAT. Please let us know anything that you enjoyed as well as anything you think we could do to improve Baby CHAT.

Your feedback will add to our Baby CHAT research. We would like to include your feedback in our report about Baby CHAT. When we do this, we make sure that the feedback is completely anonymous so no one will know who has written the comments.

Date you attended Baby CHAT:

1. Did you think the timing of the group in your pregnancy was (please circle):

Too early

About right

Too late

Please explain your answer:

.....
.....
.....
.....

2. Was the length of the group (please circle):

Too long

About right

Too short

Please explain your answer:

.....
.....
.....
.....

3. What did you enjoy about the group?

.....
.....
.....
.....

4. What information did you find most useful from the group? Why?

.....
.....
.....
.....

5. Is there anything we can do to improve Baby CHAT?

.....
.....
.....
.....

6. Was the group relevant to people with low mood? Why/why not?

.....
.....
.....
.....

7. What did you think about the 4D scan video footage? Did this give you any ideas about how your own baby is developing?

.....
.....
.....
.....

8. Do you have any other comments or feedback on the group?

.....
.....
.....
.....

Thank you for taking the time to complete this questionnaire.

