Appendix 6 – Feedback Form – Follow-Up

Participant ID:

Baby CHAT Group Feedback – Follow-Up

We would really like your feedback on whether Baby CHAT has been helpful over the weeks since you attended. Please let us know anything that you have noticed or remembered over the last few weeks.

Your feedback will add to our Baby CHAT research. We would like to include your feedback in our report about Baby CHAT. When we do this, we make sure that the feedback is completely anonymous so no one will know who has written the comments.

Date you attended Baby CHAT:

1. How much have you thought about Baby CHAT since attending (please circle):

A lot

Sometimes

Rarely/never

Please explain your answer:

.....
.....
.....

2. What have been the lasting impacts of Baby CHAT, if any:

.....
.....
.....

3. Do you think attending Baby CHAT has helped your mood? Why/why not?

.....
.....
.....

4. Do you have any other comments or suggestions about the impact of Baby CHAT over time? Is there anything else that might be helpful?

.....
.....
.....

Thank you for taking the time to complete this questionnaire.

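### The Baby CHAT feedback form in Appendix 5 does not contain the negative-effects question that Section 6 says participants will be asked

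*Combined protocol and SAP*

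**What the plan says.** Section 6 names the instrument: "Adverse event reporting will take place following the intervention via the Baby CHAT feedback form". The next sentence gives the content: "Participants will be asked if they experienced any negative effects from attending the group". What is reported is to be recorded, included in the Annual Progress Report and copied to the sponsor.

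Section 4 (Risks/burdens) relies on the same form. Information on how women experienced the group "will be collected via the feedback form to support detection of adverse events". That section also anticipates guilt and distress in some participants, and considers this more likely here than in the general population.

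Section 4 (Baby CHAT Feedback Form) describes the form as eight open items, two of them with a closed part. Its stated aim is to develop the group; detecting harm is not mentioned. The flowchart in Section 2.3 marks the feedback form and adverse events in the same post-intervention column, which agrees with Section 6.

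A separate form serves the 1-month contact: "A brief, follow-up feedback form was developed", with four items (Appendix 6).

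**The concern.** The protocol makes a specific promise about harms, and the form named to deliver it does not do so. If the study runs with Appendix 5 as printed, no woman is asked on that form whether the group affected her badly.

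What is at stake is how the harm record can be read. A feasibility study should tell the designers of the next trial whether the session distresses some women with prenatal depression. If the form yields few or no reports, a reader of the Annual Progress Report or the publication would naturally take this as reassurance, believing that everyone had been asked.

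**Working it through.** There is no figure in the plan to reproduce. The check sets the promise beside the form.

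**Step 1: read each item in Appendix 5.**

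| Item | Topic | Asks directly about negative effects? |
|---|---|---|
| 1 | Timing of the group in pregnancy | No |
| 2 | Length of the group | No |
| 3 | What was enjoyed | No |
| 4 | Most useful information | No |
| 5 | Possible improvements | No |
| 6 | Relevance to people with low mood | No |
| 7 | The 4D scan footage | No |
| 8 | "Do you have any other comments or feedback on the group" | No |

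Direct questions about negative effects: 0 of 8. Items 5, 6 and 8 could draw out a bad experience, but only if the woman raises it herself.

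**Step 2: rule out lost text.** Section 4 describes eight items, two with closed parts. Appendix 5 prints eight, with closed parts at items 1 and 2. The counts agree, so the printed form is complete on both.

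**Step 3: look for another place where the question is asked.** The promising sentence does not itself name the form, so a spoken question is conceivable. But the sentence before it names the form, Risks/burdens names it again, and no spoken or other route for putting the question to participants is described.

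**Step 4: list the other ways an event could surface.**
- The facilitator watches participants' emotional state, can raise concerns privately afterwards, and tries to reach anyone who leaves in distress (Section 4).
- Women may contact the team for a debrief (Section 4).
- Serious adverse events that become known to the team are documented (Section 6).
- The Case Report Form holds an adverse event log and is completed "at the point of participant registration to the study and after each trial procedure" (Section 9).

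The first three can reveal events. The log is where they would be written down; it does not ask anyone anything.

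**Step 5: what a form-based count would mean.** Let *k* be the number of women with a negative effect that they would report if asked, and *v* the share of them who would volunteer it unprompted. The expected count from the form as printed is *v* × *k*, with *v* anywhere from 0 to 1. The documents give no value for *v*, so a low count fits either a small *k* or a small *v*. A direct question largely removes this ambiguity and supplies a denominator: the women who answered it.

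**The case against.** The strongest reply is that this is one missing question in a study with several other safeguards. Much of that stands. A reader might infer that adverse event counts would rest wholly on stray comments. The documents do not support this, because facilitator monitoring, debrief contacts and known serious adverse events run alongside the form. Risks/burdens says the form supports detection, not that it is the only source. None of this supplies the question that Section 6 says will be asked.

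A reader might also infer that Appendix 6 breaks the same promise. It does not clearly do so. Section 6 refers to the Baby CHAT feedback form following the intervention, and the follow-up form is described separately for the longitudinal part of the study. Its items include "What have been the lasting impacts of Baby CHAT, if any" and "Do you think attending Baby CHAT has helped your mood", with room to explain, which could elicit harm. The blank adverse event cell at 1 month in the flowchart is weak evidence, since that column omits the Appendix 6 form as well.

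A third tempting reading is that item 10 of the Edinburgh Postnatal Depression Scale (thoughts of self-harm) is collected at Times 2 and 3 but goes unused. That cannot be concluded. Section 4 sends safeguarding concerns arising at any point to the Appendix 4 pathway. Only the heading of Appendix 4 and the opening text of Appendix 3 are visible, so how item 10 is handled may be set out there.

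**Conclusion.** The inconsistency stands: Section 6 promises a question, and 0 of the 8 items on the named form asks it. This rests on Appendix 5 being the form actually used and on the question not being put by some route that the protocol does not describe.

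The consequence is limited. Form-based harm data would depend on unprompted comments, alongside the other routes, and a low count would be uninterpretable. No feasibility threshold, effect size or sample size is affected. How many events would be missed cannot be estimated from the documents. No finding is made about the clinical response to distress or self-harm thoughts.

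**What to change.** Add one direct question to Appendix 5, for example: *Did you experience any negative effects or distress from attending the group? Please describe.* Update the description in Section 4 from eight items to nine (8 + 1). If the question is printed with a yes/no choice, the count of closed parts goes from two to three. Report the number answering yes beside the number who answered.

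Optionally, and as an improvement only, put the same question on the Appendix 6 form (4 + 1 = 5 items), and mark that form and an adverse event entry at 1 month in the flowchart. An effect that appears after the form due within 48 hours of the group otherwise has no scheduled question.

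The cost is one more item per form, small text edits, and perhaps a few log entries unrelated to the group.
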